8.2 Subject Identification

8.2.1 Electronic Medical Record (EMR) Query

Potential subjects will be identified via Agility (the EMR used by EHS) query. Eligible individuals are flagged in the system as they require special prophylaxis following bloodborne pathogen exposures. The research team will conduct further prescreening of individual records to further refine the list of potential subjects.

8.3 Subject Recruitment

Up to 130 subjects will be recruited from UWHealth. Specific recruitment strategies are as follows (non-comprehensive list):

8.3.1 Recruitment through Employee Health Practice

If the potential subject is agreeable, they will be provided contact information for the study team or the research team will initiate contact.

8.3.2 Email

An email invitation from EHS staff describing the study will be sent to eligible individuals.

8.3.3 Telephone Recruitment

When potential subjects contact the study team, a brief description of the study's purpose and participation requirements will be reviewed. This must also include a statement that participation is voluntary. The screener will ask the caller if s/he has any questions and about interest in participating. After all questions have been answered, the study team member will ask if the potential subject is interested in proceeding to the next step in recruitment for the study (e.g., scheduling a visit to learn more and go through the consent process, or answering some screening questions).]

8.4 Retention Strategies

Strategies for retention include:

- Appointment for the next visit will be set at the end of each visit
- Email visit reminder 3 days prior to visit and day prior if appointment is before 10am or day of visit if visit is at 10am or later.
- Recall reminders for missed appointment. Each participant will be contacted three times by email and then with two phone calls at least 2 days apart.
- Flexible study visit windows and be used with the following limits to accommodate subject schedules.

Time between visits 1 and 2	Not less than 28 days and not more than 60 days
Time between visits 2 and 3	Not less than 28 days and not more than 60 days

8.5 Early Termination and Withdrawal

Subjects are free to withdraw from participation in the study at any time upon request.

The Principal Investigator (PI) may discontinue or withdraw a subject from the study for the following reasons at her discretion:

- Pregnancy
- Subject non-compliance with study requirements (e.g., study intervention non-compliance)
- If any clinical adverse event (AE), laboratory abnormality, or other medical condition or situation occurs such that continued participation in the study would not be in the best interest of the subject
- If the subject is no longer an appropriate candidate for participation

The following actions must be taken if a subject withdraws, or fails to return for a required study visit:

- The site will attempt to contact the subject and reschedule the missed visit by email and phone as in 8.4 above and counsel the subject on the importance of maintaining the assigned visit schedule and ascertain if the subject wishes to and/or should continue in the study.

- Before a subject is deemed lost to follow-up, the investigator or designee will make every effort to regain contact with the subject as described in 8.4 above. These contact attempts shall be documented in the study file.
- If the subject continues to be unreachable, s/he will be considered to have withdrawn from the study with a primary reason of lost to follow-up. The withdrawn date is the last day of attempted contact.

9.0 STUDY AGENT (STUDY DRUG, DEVICE, BIOLOGIC, VACCINE, ETC.) AND/OR PROCEDURAL INTERVENTION

9.1 Study Agent and Control Description

Study Product

Recombinant hepatitis B vaccine with CpG adjuvant (Heplisav-B, Dynavax)

9.1.1 Source

All study drug will be provided free of charge by Dynavax, Emeryville, CA during the treatment phase.

Dynavax, Emeryville, CA will distribute hepB-CpG to UWHealth PRC. Each shipment will include a temperature-monitoring device to verify maintenance of the cold chain during transit, as well as a packing slip. On delivery of the product to the site, the person in charge of product receipt will use departmental procedures for unpacking and storing the vaccine, including checking that the cold chain was maintained during shipment (i.e., verification of the temperature indicator). The contents of the shipment will then be reviewed and verified against the packing slip, and will be documented as instructed at the initiation visit.

If the temperature-monitoring indicator reflects that the cold chain has been broken, the entire shipment must be immediately quarantined. The principal investigator will contact Dynavax for instructions.

9.1.2 Packaging and Labeling

- The vaccine will be supplied as the commercial product and labeled as such.

9.1.3 Preparation

The vaccine will be supplied as a single-dose prefilled syringe.

9.1.4 Storage and Stability

Storage Conditions

Store in a refrigerator at 2°C to 8°C (36°F to 46°F).

Do not freeze; discard if the vaccine has been frozen.

9.1.5 Dosing and Administration

HepB-CpG will be supplied as 0.5 mL single-dose, pre-filled syringes. No preparation is required. Administer as follows:

- Visually inspect the syringe for particulate matter and/or discoloration prior to administration. If either of these conditions exist, do not administer
- Gently shake the prefilled syringe
- Identify the deltoid muscle (upper arm) and cleanse the injection site with alcohol
- Insert needle (22 to 25 -gauge 1-inch needle recommended; 1 ½ inch needle recommended for those with BMI ≥ 30) at a 90 degree angle to the skin and inject entire contents of the syringe

intramuscularly. Do not inject the vaccine subcutaneously or intravenously. Care should be taken to avoid administering the injection into or near blood vessels and nerves.

- Monitor the subject for at least 15 minutes post administration]

10.0 STUDY VISITS AND PROCEDURES

10.1 Study Calendar

The procedures performed at each study visit are listed in the table below.

Procedure	Visit 1	Visit 2	Visit 3 End of study/early withdrawal
Visit Window	Day 0	Day 28- 42	Day 28-42 following visit 2
Informed Consent	X		
Review Eligibility Criteria	X		
Demographics ¹	X		
Obtain Medical History ²	X		
Vital Signs ³	X	X	X
Vaccine screening	X	X	
Vaccine administration	X	X	
Blood draw		X	X
Adverse Events			
Review/Assessment		X	X

¹ Age, sex, dates of previous hepatitis B vaccine doses and antiHBs

² Self-reported smoking history, diabetes, immunosuppression

³ vitals as standard of practice at EHS for immunization visit

10.2 Screening and Enrollment

The Screening and Enrollment visits and procedures are described in detail below.

10.2.1 Pre-screening

Potential participants will be identified and invited to participate by EHS staff. Potential participant are UWHealth healthcare workers who have received at least 5 doses of hepatitis B vaccine with aluminum adjuvant and have antiHBs < 10mIU/ml

10.2.2 Informed Consent

Preliminarily eligible subjects will be invited to EHS for informed consent and formal screening. The informed consent process will be conducted following all federal and institutional regulations relating to informed consent. Informed consent will be obtained prior to conducting any study-related activities.

The informed consent process will be performed as follows:

- The principal investigator or a co-investigator will review the informed consent form and discuss the study in detail with the potential research subject.

- The principal investigator or a co-investigator will explain the study, its risks and benefits, what would be required of the research subject, and alternatives to participation.
- The research subject will be given the opportunity to take the informed consent form home so that s/he may discuss it with family members, friends, clergy or others when possible.
- The subject will have the opportunity to ask questions and have all questions answered by the principal investigator or a co-investigator.
- The informed consent document must be signed and dated by the research subject.
- The principal investigator or a co-investigator will review the informed consent document to ensure that all fields that require a response are complete (i.e., checkbox marked yes or no, etc.) as applicable.
- The research subject will be given a copy of the signed and dated informed consent form. The original signed informed consent form is kept the study binder.

10.2.3 Enrollment

A research subject will be defined as “enrolled” in the study when they meet the following criteria:

- The subject has been consented by study staff.
- The subject and study staff have completed all screening documentation.
- The study staff has verified that the subject meets all of the inclusion criteria.
- The study staff has verified that subject meets none of the exclusion criteria.
- The subject has been assigned to the protocol by study staff.
- The subject has scheduled a study visit which can follow the informed consent process described above.

10.2.4 Screen Failure and Re-enrollment

Individuals who do not meet the criteria for participation in this trial (screen failure) because of a possible pregnancy may be rescreened. Rescreened subjects should be assigned a new subject ID number when they are re-screened.

10.3 On-Study/Follow-up Visits

After subjects have been enrolled, the On-Study/Follow-up visit and the procedures performed at each visit are described in detail below.

10.3.1 Visit Number 1

The following activities will be done during visit 1 which can directly follow the informed consent and enrollment phases.

- Limited interview for medical history to collect age, sex, race, ethnicity, and self-reported smoking history, diabetes and immunosuppression. Hepatitis B vaccine history and antiHBs dates, UWHealth department and location will be collected from Agility, the EHS EMR. (research)
- Vitals (per EHS routine)
- Vaccine screening (research)
- Vaccine administration and aftercare (research)

Visit 1 is expected to take about 45 minutes.

10.3.2 Visit Number 2

The following activities will be done during visit 2 which is done 28-42 days after visit 1.

- Vitals (per EHS routine)
- Ask about adverse events following hepB-CpG. Report to VAERS if appropriate (routine)
- Blood draw for antiHBs (research)
- Vaccine screening (research)
- Vaccine administration and aftercare (research)

Visit 2 is expected to take about 30 minutes.

10.3.3 Visit Number 3

The following activities will be done during visit 3 which is done 28-42 days after visit 3.

- Vitals (per EHS routine)
- Ask about adverse events following hepB-CpG. Report to VAERS if appropriate (routine)
- Blood draw for antiHBs (research)
- Dismiss from study participation with information that EHS employee will contact with antiHBs results (research)

Visit 3 is expected to take about 15 minutes.

10.4 Unscheduled Visits

Unscheduled visits will not occur for this study.

10.5 Early Termination/Withdrawal Visit

Subjects who are either withdrawn or terminated early from the study will have one final visit to follow up regarding adverse events.

11.0 CORRELATIVE | SPECIAL STUDIES

11.1 Biospecimen Collection Guidelines

Standard phlebotomy procedures to collect 3ml in red top with yellow ring and sent to the UWHealth Clinical Lab for antiHBs.

11.2 Assay Methodology

The UWHealth Clinical Laboratory uses a chemiluminescent immunoassay to measure antiHBs.

12.0 DATA COLLECTION, HANDLING, SHARING, AND RECORD KEEPING

12.1 Data Collection

12.1.1 Data Collection Forms

Standardized data collection forms (e.g., source documents, case report forms, standardized assessment forms, etc.) are used to ensure data collected are consistent and compliant with the protocol and IRB application.

Data collection is the responsibility of study team members under the supervision of the Principal Investigator (PI). The PI is responsible for ensuring the accuracy, completeness, legibility, and timeliness of the recorded and reported data. Data will be collected from the participant and the EHS EMR as described in Section 10.

All data collection forms must be completed in a legible manner; any missing data will be explained. Data entry errors will be corrected with a single line through the incorrect entry and the correct data is entered above/near the correction. All changes will be initialed and dated.

Data collection forms are maintained in the subject files and retained as described in Section 12.3: Records Retention.

12.2 Confidentiality and Privacy

Subject confidentiality and privacy is strictly held in trust by the participating investigators and their staff. The sponsor will have no access to the study data. This confidentiality is extended to cover testing of biological samples and to the clinical information relating to subjects. Therefore, the study protocol, documentation, data, and all other information generated will be held in strict confidence.

All research activities will be conducted in as private a setting as possible.

All study staff engaged in the conduct of this project have completed training on the protection of human subjects and the Health Insurance Portability and Accountability (HIPAA) Privacy Rule. In addition, all key personnel (i.e., Principal Investigator, individuals involved in identifying/recruiting subjects, obtaining informed consent, or interacting and intervening with subjects) have undergone Good Clinical Practice (GCP) training.

Information about study subjects will be kept confidential and managed according to HIPAA requirements. All subjects will a combined informed consent and HIPAA authorization form that includes specific privacy and confidentiality rights. Study data will be maintained per federal, state, and institutional data policies.

The investigator(s) will ensure that the identities of subjects are protected by using coded subject information. The log of subject identifying information that links subjects to their study-specific identification number will be maintained by the investigator. The log and all study records will be maintained in locked rooms and access will be limited to essential study personnel. Electronic study records/files will be stored on a School of Pharmacy server and accessed via networked computers that are password-protected with access provided only to authorized study personnel.

Authorized representatives of the following groups may need to review this research as part of their responsibilities to protect research subjects: representatives of the IRB and federal oversight agencies, such as the Food and Drug Administration (FDA). The clinical study site will permit access to such records.

Study staff may use e-mail to communicate with research subjects, if the subject has agreed to using email in the Informed Consent form. The information contained in emails will be limited to study visit time and date information and general questions. All emails to subjects will be sent from UW/wisc.edu or uwhealth accounts; personal, home or Gmail email accounts will not be used.

12.3 Records Retention

It is the investigator's responsibility to retain study essential documents for a minimum period of 7 years following completion of the study per UW-Madison institutional policy, or at least 2 years after the last approval of a marketing application in their country and until there are no pending or contemplated marketing applications in their country or at least 2 years have elapsed since the formal discontinuation of clinical development of the investigational product, whichever comes last.

12.4 Protocol Deviations

A protocol deviation is any noncompliance with the clinical trial protocol or investigational plan requirements. The noncompliance may be either on the part of the subject, the investigator, or the study site staff. As a result of deviations, corrective actions are to be developed by the site and implemented promptly.

It is the responsibility of the Principal Investigator and study staff to use continuous vigilance to identify and report deviations. The Principal Investigator is responsible for assessing whether the deviation constitutes noncompliance as defined by the reviewing IRB and will report the deviation within the timeframes posted on the HS IRB website of the discovery.

12.5 Publication and Data Sharing Policy

The Principal Investigators will work with the co-investigators to draft a manuscript for publication regarding the findings of this study. All precautions will be taken to avoid identification of an research participant in the publication.

13.0 STUDY ANALYSIS

13.1 Statistical Hypotheses

- **Primary Efficacy Endpoint(s):**

AntiHBs >10 mIU/ml following two doses of hepB-CpG

Descriptive statistics will be used to report the result, including number of responders and ratio of responders.

- **Secondary Efficacy Endpoint(s):**

AntiHBs >10 mIU/ml following two doses of hepB-CpG

Descriptive statistics will be used to report the result, including number of responders and ratio of responders.

Proportion of participants who are nonresponders with each risk factor and develop a multivariate model

Descriptive statistics will be used to report the result for each risk factor, including number of responders and ratio of responders. Multivariate analysis will be used to develop a model.

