Total Number of Subjects	Up to 130 individuals will be recruited and enrolled.
Study Population	Healthcare workers who have received at least 5 doses of hepatitis B vaccine with aluminum adjuvant and have antiHBs < 10mIU/ml.
Statistical Methodology	We will count the number of individuals who seroconvert and have anti-HBs >10 mIU/ml and report a ratio with the total number immunized as the denominator. We will develop a multivariate model to predict hepB-CpG response which will include age, sex, smoking status, diabetes, and immunosuppression as variables.
Estimated Subject Duration	The duration of the study for each subject is approximately 8 weeks.
Estimated Enrollment Period & Study Duration	Study enrollment and follow-up will occur over 12 months.

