6.0 STUDY OBJECTIVES AND ENDPOINTS

Objectives	Endpoints
Primary To measure the number of healthcare workers who failed to respond to 5 or more doses of hepatitis B vaccine with aluminum adjuvant who will respond to hepatitis B vaccine with CpG adjuvant series	antiHBs > 10mIU/ml after completion of the series
Secondary To measure the number of healthcare workers who respond to a single dose of hepB-CpG	antiHBs > 10mIU/ml after one dose of hepB-CpG
To determine risk factors associated with hepatitis B vaccine nonresponse, including age, smoking status, sex, diabetes, immunosuppression	Proportion of participants who are nonresponders with each risk factor and develop a multivariate model

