13.3 Subject Population(s) for Analysis

Analyses will include all individuals who received at least one dose of hepB-CpG. We will also do a per-protocol analysis for hepB-CpG one dose and two doses.

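### Response (>10 mIU/ml) is not the complement of the protocol's own non-response rule (<10), so a titre of exactly 10 counts as a failure; 13.1 also misprints the secondary endpoint

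*Combined protocol and SAP*

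**What the plan says.** **Response after hepB-CpG.** Section 13.1 states the primary endpoint as "AntiHBs >10 mIU/ml following two doses of hepB-CpG". The Synopsis (3.1, Endpoints) and Section 6.0 use the same strict inequality for the two-dose and the single-dose endpoints. The Statistical Methodology row of the Synopsis says how the ratio is formed: count those who "have anti-HBs >10 mIU/ml and report a ratio with the total number immunized as the denominator".

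**Non-response to the earlier vaccine.** Wherever the protocol gives this a value, it is strictly below 10 mIU/ml: the Synopsis (Main Inclusion Criteria and Study Population), the schematic in 3.2, the account of employee screening in 5.1, the design in 7.1, inclusion criterion 3 in 8.1, and pre-screening in 10.2.1.

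**Risk factors.** Section 6.0 gives the endpoint as "Proportion of participants who are nonresponders with each risk factor and develop a multivariate model". Section 13.1 says "Descriptive statistics will be used to report the result for each risk factor, including number of responders and ratio of responders", and the Synopsis says "We will develop a multivariate model to predict hepB-CpG response". None of these lines attaches a cut-off to the word nonresponder.

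**Secondary endpoint.** Section 6.0 has "antiHBs > 10mIU/ml after one dose of hepB-CpG", and the Synopsis agrees. Section 13.1 instead prints the two-dose line again under its secondary heading. Section 13.3 nevertheless plans a one-dose analysis ("We will also do a per-protocol analysis for hepB-CpG one dose and two doses"), and 13.4 also covers response to one dose.

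**The concern.** The study asks whether people classed as non-responders on one marker become responders on the same marker. A reader therefore expects the two classes to be complements, and at one value they are not. Someone whose titre had been 10 after the aluminum-adjuvanted doses would not have been eligible as a non-responder. Someone who reaches 10 after hepB-CpG is counted as not having responded.

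The cut-off fixes the numerator of the primary ratio, the numerator of the single-dose ratio and the outcome of the response model. The study is open label and has no comparator. If a 10 appeared and the cut-off were revised afterwards, the change would look driven by the result.

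The second item is a contradiction inside the analysis section: taken literally, 13.1 makes the secondary endpoint identical to the primary.

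**Working it through.** The plan states no power calculation or test for this endpoint (13.2 offers the vaccine to all known eligible workers), so there is no derived figure to reproduce. The check compares the text and then sizes the effect per person.

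**Step 1: the rules at, below and above 10**

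| Titre (mIU/ml) | Entry rule (3.1, 3.2, 5.1, 7.1, 8.1, 10.2.1) | Endpoint rule (3.1, 6.0, 13.1) |
|---|---|---|
| below 10 | non-responder | not a response |
| exactly 10 | not a non-responder | not a response |
| above 10 | not a non-responder | response |

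The rules disagree only in the middle row. No section uses ≥10 or ≤10 for antiHBs. A lost symbol in the PDF text is an unlikely explanation: 9.1.5 prints ≥ correctly for BMI, and the strict sign recurs in every statement of the endpoint.

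**Step 2: how the primary ratio treats a 10**

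Response rate = (number with titre >10) / (total immunized). A participant at exactly 10 adds 0 to the numerator and 1 to the denominator, and so is a failure.

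**Step 3: size per participant**

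Inputs: the enrolment cap of 130 (3.1, Total Number of Subjects) and the staff estimate of about 100 eligible workers (16.2). Moving one person from failure to response changes the rate by 1/N:

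- N = 130: 1/130 = 0.77 percentage points
- N = 100: 1/100 = 1.0 percentage point

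**Step 4: scale against sampling error**

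The number of participants at exactly 10 is not in the documents. Taking 0 to 3 purely as an assumption, and starting from 70% (the response hypothesized in 5.1), the rates with exact (Clopper-Pearson) 95% intervals are:

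| Number at exactly 10, recounted as response | N = 100 | N = 130 |
|---|---|---|
| 0 | 70/100 = 70.0% (60.0 to 78.8) | 91/130 = 70.0% (61.3 to 77.7) |
| 1 | 71/100 = 71.0% (61.1 to 79.6) | 92/130 = 70.8% (62.2 to 78.4) |
| 3 | 73/100 = 73.0% (63.2 to 81.4) | 94/130 = 72.3% (63.8 to 79.8) |

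**Step 5: the secondary endpoint**

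| Section | Secondary response endpoint |
|---|---|
| 3.1 Synopsis | after a single dose |
| 6.0 | after one dose |
| 13.1 | after two doses (same line as the primary) |
| 13.3, 13.4 | one-dose analysis planned |

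Section 13.1 stands alone. The blood draw needed for the single-dose endpoint is scheduled at Visit 2 (10.1, 10.3.2).

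**The case against.** The best defence is that nothing is undefined. The endpoint is strictly above 10 wherever it is stated, the ratio has a clear denominator, and every measured titre falls on one side. Entry and outcome rules apply at different times, nobody enters at 10, and no section requires them to be complements. The strict sign is also the conservative choice for a response rate. Most of this stands. A reader might infer that a titre of exactly 10 has no class at all, but the Synopsis ratio makes it a failure. What the defence does not answer is that the same titre on the same marker is treated differently before and after the study vaccine, with no reason given.

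The practical effect is also unproven. Section 11.2 names only the assay type. A reader might model the count, for example with log-normal titres, 70% of reported results above 10 and an SD of 0.5 to 1.5 log10. Whole-number reporting then gives 1.0 to 3.0 people at exactly 10 out of 100, which would turn 70% into 71% to 73%. One-decimal reporting under the same model gives 0.10% to 0.30%, or at most 0.3 of a person out of 100. Distribution, SD and rounding are all invented for the exercise, and 5.1 does not attach a cut-off to its 70%. The documents therefore do not support 71% to 73% as an expected effect.

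No decision turns on the difference: 13.1 and 13.4 plan descriptive counts and ratios, with no test or success threshold, and the shifts above lie well inside the intervals.

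On 13.1, a reader might infer that the single-dose analysis has been dropped. Sections 3.1, 6.0, 13.3 and 13.4 show that it has not.

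**Conclusion.** The point holds and is minor. As written, a post-vaccine titre of exactly 10 mIU/ml is a failure in the primary and single-dose ratios, while the protocol's own rule for the earlier vaccine would not call it non-response. Each such participant costs 0.77 points (N = 130) to 1.0 point (N = 100) of response rate. The total is unknown without the laboratory's reporting precision and the titre spread, and it is nil if nobody reads exactly 10. The mismatch in the text is certain; an effect on the result is only possible.

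The secondary line in 13.1 is wrong against the rest of the protocol. It is recoverable: no analysis is lost and no number changes.

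**What to change.** 1. Before results are seen, define response as antiHBs ≥10 mIU/ml in the Synopsis (both Endpoints lines and Statistical Methodology), Section 6.0 and Section 13.1. This is the exact complement of the <10 rule already used at entry, which stays as it is. Keeping >10 and defining nonresponder as ≤10 would give the word a cut-off but leave the mismatch with entry.
2. State that the risk-factor tables and the model use the same definition: responder ≥10, nonresponder <10.
3. In 13.1, replace the secondary line with response following a single dose of hepB-CpG, measured on the Visit 2 draw taken before dose 2, to agree with 3.1, 6.0, 13.3 and 13.4.

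The cost is a handful of line edits in three sections, with no added visits, samples or assays. Items 1 and 2 alter the endpoint definition at one value, so they should be made and dated before results are seen. Item 3 is wording only.
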